Cover letter for NCT03328143

Protocol ID 17.101

Protocol title Feasibility of Aromatherapy in an Awake Craniotomy Environment

Date: November 21, 2020

The document listed as Protocol Synopsis reflects the full Study Protocol and Statistical Analysis Plan. As this was a feasibility study, we did not prepare a formal study protocol or statistical analysis plan.

Thank you,

[name]

Protocol Summary

Title	A Feasibility Study of Lavender Aromatherapy in an Awake Craniotomy Environment
Principal Investigator	[name]
Research Question(s)	Is it possible to utilize lavender aromatherapy during awake craniotomy
Study Aims and Hypotheses	
H_0: Aromatherapy is technically feasible during awake neurosurgical procedures
 
Aim 1: To determine the percent of patients who would consent to participate
 
Aim2: To determine the study completion rate for the consented patients

Primary Endpoint(s)	
 1. The number of patients consenting to participate 2. The number of patients completing the study
Secondary Endpoint(s)	
 1. Anxiety before and after lavender aromatherapy intervention 2. Pain before and after lavender aromatherapy intervention 3. Patient's expectation of lavender aromatherapy 4. Patient satisfaction with lavender aromatherapy
Study Design	Open label, single arm
Study Population	
Inclusion Criteria: an adult patient undergoing clinically indicated cranial neurosurgical procedure
 
Exclusion Criteria: allergy to lavender (Lavandula angustifolia); aversion to lavender scent; history of asthma or COPD; pregnancy; history of contact dermatitis following exposure to cosmetic fragrances

Treatment	Inhalation of lavender from a nasal inhaler, prior to the start of surgery and every 30 minutes thereafter, or if requested by the patient
Method of Randomization	N/A
Sample Size Calculation	N/A
Outcome Measures	VAS-A, VAS-P, expectancy questionnaire, POPM tool
Statistical Analysis	Demographic characteristics were noted using appropriate descriptive statistics for all

	categorical and continuous variables. As both VAS-A and VAS-P were assessed multiple times for the same patients, mean scores of these measures were compared using the repeated measures analysis of variance (ANOVA), including multivariate analysis of variance (MANOVA) tests in the general linear model. Expectancy questionnaire responses were analyzed using a 2-sided, paired t-test. Mean POPM scores were compared using an independent t-test. An alpha of 0.05 was used for all statistical tests, and all analyses were done using SAS® 9.4 (SAS Institute Inc., Cary, NC).
Interim Analysis	N/A
Subgroup Analysis	N/A
Safety	This trial used the U.S. Department of Health and Human Services' Common Terminology Criteria for Adverse Events, Version 4.0 (published May 28, 2009; revised June 14, 2010) for toxicity and adverse event reporting.
Closure	The results will be submitted to medical meetings and peer reviewed journals

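### Does the consent endpoint need a stated denominator, and do the two primary endpoints need a written analysis with intervals?

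*Combined protocol and SAP*

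**What the plan says.** All the relevant text is in the Protocol Summary and its cover letter.

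- **Study Aims and Hypotheses:** "Aim 1: To determine the percent of patients who would consent to participate" and "Aim2: To determine the study completion rate for the consented patients".
- **Primary Endpoint(s):** "The number of patients consenting to participate" and "The number of patients completing the study".
- **Outcome Measures:** "VAS-A, VAS-P, expectancy questionnaire, POPM tool". Consent and completion are not listed.
- **Statistical Analysis:** it opens with "Demographic characteristics were noted using appropriate descriptive statistics for all" categorical and continuous variables. It then gives repeated measures ANOVA and MANOVA for the two VAS scales and a paired t-test for expectancy. It ends with "Mean POPM scores were compared using an independent t-test. An alpha of 0.05 was used for all statistical tests". Neither primary endpoint appears.
- **Sample Size Calculation, Interim Analysis and Subgroup Analysis:** each is marked not applicable. No target rate or feasibility threshold is given anywhere.
- **Cover letter:** because this was a feasibility study, "we did not prepare a formal study protocol or statistical analysis plan". The synopsis is the whole plan, so the detail is not held elsewhere.

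**The concern.** A count of consenting patients does not give a percentage until someone says what it is a percentage of. The plan leaves open whether the base is everyone screened, everyone approached, or only eligible patients. Two analysts holding the same log could therefore report different consent rates for the study's first aim.

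The second worry is one of balance. Every named test is on a secondary measure, and the two quantities that define feasibility have no described summary and no planned interval. With no sample size calculation, an interval would be the usual guide to how precisely feasibility was measured. At stake are the comparability of the headline consent rate and the reader's sense of its precision.

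**Working it through.** **Inputs.** The documents give no number of patients screened, approached, eligible, consenting or completing, and no planned sample size. There is no stated figure to reproduce. Every count below is assumed for illustration.

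**1. Set each aim beside its endpoint.**

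| | Scale set by the aim | Base set by the aim | Endpoint supplies | Left open |
|---|---|---|---|---|
| Aim 1 | percentage | not stated | numerator | base |
| Aim 2 | rate | consented patients | numerator; endpoint 1 is the base | meaning of completion |

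The contrast between percentage and count is nominal, because the aim sets the scale and the endpoint supplies the numerator. What is really open for Aim 1 is the base. The Study Population row makes eligible patients a natural reading, since an excluded patient cannot enter, but it does not say so. For Aim 2 the two primary endpoints are numerator and denominator, although the plan does not define what counts as completing.

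**2. How far can the choice of base move the consent rate?** Let A be patients approached, E the eligible patients among them, and C those consenting, with no excluded patient consented. Then

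C/E − C/A = [(A − E)/A] × (C/E),

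which is the share of approached patients excluded, times the consent rate among eligible patients. Take A = 30 and C = 20, with exact (Clopper-Pearson) 95% intervals:

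| Excluded | Base | Rate | Exact 95% CI | Shift from 20/30 |
|---|---|---|---|---|
| base is all approached | 30 | 66.7% | 47.2 to 82.7% | – |
| 3 | 27 | 74.1% | 53.7 to 88.9% | 3/30 × 20/27 = 7.4 points |
| 5 | 25 | 80.0% | 59.3 to 93.2% | 5/30 × 20/25 = 13.3 points |

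The shift is driven by the assumed exclusion share (3/30 = 10%, 5/30 = 17%). With no exclusions it is zero. In both examples it is also small beside the interval at this sample size: for 20/30 the width is 82.7 − 47.2 = 35.5 points.

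**3. Does Aim 2 need a planned interval?** Once the two counts are reported, any reader can compute one. For an assumed 90% completion:

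- 9/10: 55.5 to 99.7%
- 18/20: 68.3 to 98.8%
- 27/30: 73.5 to 97.9%

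These intervals describe precision. The plan has no threshold to hold them against, so none of them would alter a conclusion the plan sets out to draw.

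**4. Is any stated item wrong?** No. There is no sample size, power, target rate or decision rule for the missing base to upset, and the tests on secondary measures do not depend on it.

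**The case for a change.** The strongest case for a change is that consent and completion are the study's results, so they most deserve a definition. The plan found room to specify analyses for VAS-A, VAS-P, expectancy and POPM, so brevity does not fully explain the omission. The opening sentence on descriptive statistics does not fill the gap, because its subject is demographic characteristics. The cover letter rules out a fuller plan elsewhere. The base also matters in substance: aversion to the scent is an exclusion criterion, so a patient who dislikes lavender could be logged as ineligible, outside an eligible base, or as declining, inside it. Stating the bases and adding exact intervals would need no new patients.

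The textual points stand, and so does the scent-aversion example as a real ambiguity. They do not show that the plan would mislead. A consent rate is ordinarily reported with its numerator and denominator, which resolves the ambiguity for that reader. A descriptive feasibility count needs no hypothesis test, so finding tests only on secondary measures is not a fault. Writing in two consent rates without naming one as primary would leave the headline figure as open as before, and restating completion over consented would still not define completion. The letter is dated November 2020 and the analysis text is in the past tense, so a log of approaches cannot now be created if none was kept. What remains is a matter for the results report.

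**Conclusion.** No change to the plan follows. The consent base is unstated and the primary endpoints have no described summary, but this is missing detail of a kind that analysts fill sensibly. Aim 1 sets a percentage, Aim 2 sets a rate among consented patients, and reporting the counts behind each lets a reader see the base used and compute an interval. No stated figure, threshold or rule is wrong.

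The size is unknown from the documents. The shifts of 7.4 and 13.3 points rest wholly on assumed counts (30 approached, 20 consenting, 3 or 5 excluded, none of those excluded consenting) and cannot be read as evidence about this trial. The conclusion assumes that the report gives numerators and denominators for both rates and says what was counted as completion. It would be different if the plan had set a feasibility threshold, because the choice of base could then decide whether the threshold was met. It sets none.

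### Does the missing word "awake" in the inclusion criterion let non-awake patients into the consent and completion figures?

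*Combined protocol and SAP*

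**What the plan says.** The summary is titled "A Feasibility Study of Lavender Aromatherapy in an Awake Craniotomy Environment", and the cover letter gives a similar title. The research question is "Is it possible to utilize lavender aromatherapy during awake craniotomy", and H_0 reads "Aromatherapy is technically feasible during awake neurosurgical procedures".

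The Study Population row admits "an adult patient undergoing clinically indicated cranial neurosurgical procedure". It excludes lavender allergy and then "aversion to lavender scent; history of asthma or COPD; pregnancy; history of contact dermatitis following exposure to cosmetic fragrances".

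The two primary endpoints are counts: patients who consent and patients who complete. The percentages come from the aims. Aim 1 is "To determine the percent of patients who would consent to participate", with no denominator named. Aim 2 is completion among those who consented.

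The cover letter states that "The document listed as Protocol Synopsis reflects the full Study Protocol and Statistical Analysis Plan", and that "As this was a feasibility study, we did not prepare a formal study protocol or statistical analysis plan".

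**The concern.** The eligibility row is wider than the question. The study asks about awake surgery, but the criterion accepts any clinically indicated cranial operation in an adult. A thin synopsis is usually excused because a full protocol carries the detail, and here the cover letter rules that out.

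In a feasibility study, the people who are eligible and approached largely determine the answer. A patient scheduled for non-awake surgery who was approached would count towards consent. If that patient agreed, he or she would also enter the Aim 2 denominator, which is everyone who consented. The results would then describe a mixed group, while the question concerns awake patients only. The documents alone would not let a reader rule this out.

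**Working it through.** The plan states no sample size, rate or threshold, so there is no figure to reproduce. The check is a comparison of text.

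**Where the study is described as awake**

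| Place | Scope |
|---|---|
| Cover letter, protocol title | awake craniotomy |
| Protocol Summary, Title | awake craniotomy |
| Protocol Summary, Research Question(s) | awake craniotomy |
| Protocol Summary, H_0 | awake neurosurgical procedures |

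Count: 1 + 1 + 1 + 1 = 4.

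**Eligibility criteria**

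| Criterion | Mentions awake status or anaesthesia? |
|---|---|
| Inclusion: adult, clinically indicated cranial procedure | No |
| Exclusion: lavender allergy | No |
| Exclusion: dislike of the scent | No |
| Exclusion: asthma or COPD | No |
| Exclusion: pregnancy | No |
| Exclusion: fragrance contact dermatitis | No |

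Count: 0 of 1 + 5 = 6. The literal mismatch is therefore real, and it is not a product of redaction or broken extraction.

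**What the other rows imply.** The Treatment row has the patient inhale before surgery starts, again every 30 minutes, and on request. The first dose could be given to anyone. The repeats, and above all the doses on request, presuppose a patient who can inhale on cue and ask for more while the operation is under way. Taken with the four statements of scope, the synopsis has one sensible reading: the cranial procedures in the eligibility row are the awake ones.

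**What would have to happen for a result to change.** A non-awake patient would have to be approached (for the Aim 1 percentage) or to consent (for the count of consenting patients and the Aim 2 denominator). Suppose a share q of consenters were non-awake and could not complete, and awake patients completed at rate c. The observed completion rate would be c × (1 − q). Both values are assumptions, as the documents give neither. With c = 0.90:

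- q = 0: 0.90 × 1.00 = 0.90, no effect
- q = 0.10: 0.90 × 0.90 = 0.81
- q = 0.25: 0.90 × 0.75 = 0.675
- q = 0.50: 0.90 × 0.50 = 0.45

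This shows the mechanism only. Nothing in the documents supports any q above zero, and whether a non-awake patient could count as a completer is not stated either. The consent percentage could move in either direction or not at all.

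**The case for a change.** The strongest case for a change is that a title is not an eligibility criterion. Consent comes before treatment, so the Treatment row screens nobody out at the point of approach. The stated scopes also differ: the research question says craniotomy, while H_0 says neurosurgical procedures, so a reader who supplies the missing restriction must choose between them. Adding a word costs almost nothing, and a reported count of non-awake patients, even zero, would settle the matter.

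Much of this is accurate. The eligibility text is looser than it should be, the two awake scopes do differ, and no other document closes the gap. What does not follow is that the study would have run or been analysed differently. Staff recruiting for a trial of aromatherapy in awake craniotomy would not read the row as an invitation to approach patients who will be unconscious. The difference between the two scopes does not admit non-awake patients, since both are awake.

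The timing also limits what a change could achieve. The cover letter speaks of the study in the past tense, as does the Statistical Analysis row, so rewording the criterion cannot alter who was enrolled. A count of non-awake patients is a matter for the report of results, and it depends on the planned procedure type having been recorded, which the documents do not say.

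The link to the consent percentage is also indirect. Aim 1 does not say whether its base is patients approached, screened or eligible. That is a separate gap, and it would remain if the criterion said awake.

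**Conclusion.** The inconsistency is genuine but clerical: 4 statements of awake scope and 0 of 6 criteria that carry it. The rest of the synopsis supplies the restriction, and writing it into the criterion would record what the investigators would do anyway. No effect is shown on the two primary counts or on the percentages in Aims 1 and 2. If everyone approached was scheduled for awake surgery, the effect is exactly nil.

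This rests on two assumptions: that recruitment followed the stated title and question, and that the Treatment row describes what was done in theatre. The documents support both as intent, but they contain no enrolment data that would confirm them. Evidence that a non-awake patient had been approached or consented would reopen the point. As the documents stand, no change to the plan is needed.

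### Excluding patients for aversion to the scent screens on a likely reason to refuse, so the Aim 1 consent percent overstates acceptability if those patients are left out of its denominator

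*Combined protocol and SAP*

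**What the plan says.** All the relevant text is in the Protocol Summary of the combined protocol and SAP.

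- **Research Question(s):** "Is it possible to utilize lavender aromatherapy during awake craniotomy".
- **Study Aims and Hypotheses:** "Aim 1: To determine the percent of patients who would consent to participate". The denominator is not defined as eligible, screened or approached patients. Aim 2, by contrast, names its denominator: "To determine the study completion rate for the consented patients".
- **Primary Endpoint(s):** the first is a count, "The number of patients consenting to participate".
- **Study Population:** the inclusion criterion is "an adult patient undergoing clinically indicated cranial neurosurgical procedure". The exclusions include "aversion to lavender scent; history of asthma or COPD; pregnancy", together with lavender allergy and previous contact dermatitis from fragrances.
- **Statistical Analysis:** no analysis of the consent percent is described. The alpha of 0.05 applies to tests of other outcomes and has no bearing here.

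The plan does not say when or how aversion is ascertained, whether that happens before or after the approach for consent, or whether patients excluded for it are logged and reported.

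**The concern.** Allergy, asthma, COPD, pregnancy and fragrance dermatitis can all be read as safety exclusions. Aversion to the scent cannot be read that way so easily: it is a preference, and one of the most direct reasons to refuse inhaled lavender. In an efficacy trial the exclusion would be unremarkable. Here willingness to consent is itself a primary aim, so an eligibility rule acts on a direct determinant of the outcome.

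The practical risk lies in how refusals are classified. A patient who mentions disliking lavender could be recorded as ineligible, while another with the same dislike who simply declines would be recorded as a refusal. Nothing in the plan prevents this.

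Naming a denominator does not settle the matter by itself. Eligible patients are a conventional choice, and that choice would remove averse patients by rule. What is at stake is the meaning of the consent percent: whether it describes acceptability among patients having these procedures, or only among those without a declared aversion. Completion, expectation and satisfaction are measured in the same narrower group.

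**Working it through.** The plan states no consent rate, prevalence of aversion, sample size or feasibility threshold, so there is no figure of its own to reproduce. The check is algebra with assumed inputs.

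**Definitions**, among patients who meet every criterion other than aversion:

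- a = share who are averse to the scent
- c = consent rate among the rest
- k = share of averse patients who would consent if asked

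**Formulas**

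- Percent if averse patients are left out: c
- Percent among all otherwise eligible patients: c(1 − a) + ka
- Overstatement: c − [c(1 − a) + ka] = a(c − k)

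The overstatement is positive when k < c and zero when k = c. If averse patients stay in the denominator, because everyone screened or approached is counted, there is no overstatement from this source.

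**Main illustration**, assuming c = 70%:

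| a | Percent, k = 0 | Overstatement, k = 0 | Overstatement, k = 25% |
|---|---|---|---|
| 5% | 0.70 × 0.95 = 66.5% | 3.5 points | 0.05 × 0.45 = 2.25 points |
| 10% | 0.70 × 0.90 = 63.0% | 7.0 points | 0.10 × 0.45 = 4.5 points |
| 15% | 0.70 × 0.85 = 59.5% | 10.5 points | 0.15 × 0.45 = 6.75 points |

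**Wider range**, assuming c = 50% to 90% and a = 2% to 20%:

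- k = 0: from 0.02 × 0.50 = 1.0 point to 0.20 × 0.90 = 18.0 points
- k = 25%: from 0.02 × 0.25 = 0.5 points to 0.20 × 0.65 = 13.0 points

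**In counts.** Take 100 otherwise eligible patients, of whom 10 are averse and 63 of the other 90 consent. The percent is 63/90 = 70% without the averse patients and 63/100 = 63% with them counted as not accepting. The number consenting is 63 either way, so the choice of denominator affects the Aim 1 percent and not the count listed as the endpoint.

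**Use of two figures.** For any k between 0 and c, acceptance among all otherwise eligible patients lies between c(1 − a) and c. Reporting both percents therefore brackets it without having to know k.

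**The case against.** The strongest objection is that no bias has been shown. Aim 1 does not specify an eligible-only denominator, and no screening workflow is described. A reader might infer that the plan does overstate the consent percent, but the documents support only the conditional statement. With everyone screened or approached in the denominator, the effect disappears.

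Other stronger readings are tempting and also fail:

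- *The sample is enriched for people who like lavender.* Neutral patients remain eligible; only averse ones are removed.
- *The direction is always upward.* This needs averse patients to be dropped and k < c. The second condition is likely, but it is an assumption.
- *The primary endpoint is biased.* The listed endpoint is a count with no denominator. The point concerns the percent in Aim 1.
- *The figure counting averse patients as refusers should be the primary result.* Consent among eligible patients is a legitimate feasibility measure: of those who could receive the intervention, how many agree? Consent to take part in a study is also not the same as acceptance of lavender. Replacing one estimand with the other is debatable, and nothing in the plan requires it.

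Consequences are limited too. With "Sample Size Calculation N/A" and no feasibility threshold, no stated decision turns on a few points.

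All of this stands and narrows the point. It leaves untouched that a preference-based exclusion screens on a determinant of consent, and that an eligible-only denominator would build this into the percent. That percent would be valid for patients without aversion; the difficulty is reading it as acceptability in all otherwise eligible patients.

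**Conclusion.** The point holds in conditional form. If patients excluded only for aversion are left out of the denominator, the Aim 1 percent overstates acceptability among otherwise eligible patients by a(c − k). With assumed c = 70%, k = 0 and a = 5% to 15%, that is 3.5 to 10.5 points; less extreme assumptions can bring it to a point or below, and counting everyone screened or approached brings it to zero. None of the inputs is in the documents, so the actual size is unknown. It is a cheap improvement to what the study can conclude about acceptability, and not evidence that the design is invalid.

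**What to change.** Keep the exclusion as it is. Then:

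1. Record in the screening log when aversion to the scent is the only reason for exclusion, and report that number.
2. Define the denominator for Aim 1. Report the consent percent among fully eligible patients and, beside it, the percent with patients excluded only for aversion added to the denominator as not accepting.
3. State that the completion, expectation and satisfaction results apply to patients without aversion to the scent.

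The Statistical Analysis text is written in the past tense. If screening has ended, items 1 and 2 depend on whether the reason for exclusion was kept; if it was not, the report should say so as a limitation. Item 3 can be done in any case.

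The cost is one extra screening-log field, a sentence or two of endpoint and reporting text, and a second consent figure slightly less favourable than the first. No additional patients, visits or procedures are needed.

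### The VAS-A and VAS-P endpoints are before versus after lavender, but the plan names no before/after contrast, estimate or interval, and an overall test across more than two times would not test that endpoint

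*Combined protocol and SAP*

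**What the plan says.** The Secondary Endpoint(s) row lists "Anxiety before and after lavender aromatherapy intervention" and "Pain before and after lavender aromatherapy intervention". The Treatment row has lavender inhaled "prior to the start of surgery and every 30 minutes thereafter, or if requested by the patient", so a patient may have several inhalations.

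The Statistical Analysis row gives the reason for its method, "As both VAS-A and VAS-P were assessed multiple times for the same patients", and then the method: "mean scores of these measures were compared using the repeated measures analysis of variance (ANOVA"). The row also names MANOVA tests for these scores. It adds that "An alpha of 0.05 was used for all statistical tests". A paired t-test appears in that row only for the expectancy questionnaire.

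The summary does not give the number or timing of VAS assessments, the levels of the within-patient factor, the scores that count as before and after, or any contrast, estimate or confidence interval. The cover letter says this synopsis stands for the whole protocol and SAP, so these items are not set out elsewhere.

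**The concern.** A before/after endpoint calls for a comparison of two defined quantities within a patient. A repeated measures ANOVA or MANOVA across several times asks whether any mean differs from any other. With only two times the questions coincide; with more they do not. Pain or anxiety could rise during the operation and return to its starting level. The overall test would then tend to be significant although before equals after, and its p-value could be reported as the endpoint result.

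A p-value alone also gives neither the direction nor the size of the change, which are what a feasibility study most needs in order to plan the next trial. Because inhalations recur, before and after could be taken around each inhalation or across the whole procedure, and these can give different answers in the same data.

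**Working it through.** **Inputs.** The documents give no sample size, number of times, SD, correlation or effect size, so there is no planned figure to reproduce. Everything below is assumed except alpha 0.05, which is the plan's. Scores are multivariate normal with SD 1.

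**1. Before equals after, with a rise in between.** n = 20, k = 4 or 6 times, AR(1) correlation 0.6. The first and last means are 0 and all others 0.5.

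For MANOVA (one-sample Hotelling test of equal means) the power is exact, from a noncentral F with k−1 and n−k+1 df and

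λ = n [μ′Σ⁻¹μ − (1′Σ⁻¹μ)² / (1′Σ⁻¹1)].

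For AR(1) at 0.6, Σ⁻¹ is 1/(1 − 0.36) = 1.5625 times a tridiagonal matrix with end diagonals 1, interior diagonals 1.36 and off-diagonals −0.6.

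- k = 4: μ′Σ⁻¹μ = 1.5625 × (0.68 − 0.30) = 0.59375; 1′Σ⁻¹μ = 1.5625 × 0.16 = 0.25; 1′Σ⁻¹1 = 1.5625 × 1.12 = 1.75. So λ = 20 × (0.59375 − 0.0625/1.75) = 11.16. With 3 and 17 df, rejection is 70%.
- k = 6: μ′Σ⁻¹μ = 1.5625 × (1.36 − 0.90) = 0.71875; 1′Σ⁻¹μ = 1.5625 × 0.32 = 0.5; 1′Σ⁻¹1 = 1.5625 × 1.44 = 2.25. So λ = 20 × (0.71875 − 0.25/2.25) = 12.15. With 5 and 15 df, rejection is 60%.

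By simulation, univariate ANOVA without a sphericity correction rejects in about 66 to 70%, and with Greenhouse-Geisser correction in 54 to 64%. The last-minus-first contrast has mean 0 and rejects in about 5%. At n = 15 the uncorrected ANOVA figure is 52 to 55%, and at n = 30 it is 86 to 89%.

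**2. Limit: two times only.** With k = 2, n = 20, correlation 0.5 and a 0.5 SD change, ANOVA, MANOVA and the paired t-test are the same test, each with about 56% power. The mismatch needs more than two times.

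**3. Power against first-versus-last.** Steady decline of 0.6 SD over 8 times, exchangeable correlation 0.6, n = 20.

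- Overall tests: the sum of squared deviations of the means is (0.6/7)² × 42 = 0.3086, so λ = 20 × 0.3086/0.4 = 15.43. ANOVA (7 and 133 df) has about 81% power; MANOVA (7 and 13 df) has 59%.
- Contrast: the SD of the change is √(2 × 0.4) = 0.894, the noncentrality is 0.6/0.894 × √20 = 3.0, and power with 19 df is 81%.

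MANOVA loses power here; ANOVA does not.

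**4. Power against a matched contrast.** n = 20, exchangeable correlation 0.5, simulated.

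| Effect | k | ANOVA | MANOVA | Matched contrast |
|---|---|---|---|---|
| 0.4 SD drop in each before/after pair | 4 / 6 / 8 | 52 / 62 / 71% | 45 / 49 / 50% | 67 / 83 / 93% |
| 0.5 SD sustained drop from baseline | 4 / 6 / 8 | 59 / 56 / 53% | 51 / 43 / 34% | 74 / 78 / 80% |

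For the sustained drop, a first-versus-last contrast has about 57%, level with ANOVA.

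**5. The definition matters.** With a 0.4 SD drop in each pair (n = 20, k = 6, AR(1) 0.5), the within-pair contrast rejects in 91%, first-versus-last in 23%, and baseline against the later mean in 17%. With every pair equal but 0.8 SD drift across surgical stages, the same three contrasts reject in 5%, 69% and 52%. Before/after is not one quantity until it is defined.

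**The case against.** The plan does not call its test an omnibus test or say that it covers all times. A two-level before/after factor would make repeated measures ANOVA identical to a paired t-test, and a repeated-measures model is a sensible frame for recurrent before/after ratings. This stands, so a reader who infers that the plan definitely specifies the wrong test goes further than the text. The weaker claim holds: several assessments are the stated reason for the method, a paired test is named only for another outcome, and a two-level factor would still need a rule for collapsing several scores into two.

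A reader might also infer a general loss of power. Steps 3 and 4 do not support that: the loss depends on the test, the number of times and the contrast used for comparison.

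The 60 to 70% is not an error rate of the test. It rightly rejects equal means when they differ; the fault would lie in reading that result as a before/after change. The rise itself is an assumption.

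Drift over surgery is a tempting further argument. It arises from the uncontrolled single-arm design and affects a first-versus-last contrast too (step 5), so it does not count against ANOVA in particular.

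Finally, the primary endpoints are the numbers consenting and completing, and no formal SAP was prepared. That lowers the severity but does not remove the mismatch.

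**Conclusion.** The concern holds as a minor point. The two VAS endpoints are before/after comparisons, and the plan never defines the comparison or asks for an estimate of it. If the factor has more than two times, the overall time test does not test the endpoint, and under the assumptions in step 1 the rejection rates at n = 20 differ by a factor of about 12 to 14 (60/5 to 70/5). The logical mismatch does not depend on those assumptions; its size depends on them entirely. Lower power is a possible secondary cost, chiefly with MANOVA. Two of the four secondary endpoints are affected and neither primary endpoint is.

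**What to change.** For each of VAS-A and VAS-P, name the before score (the last before the first inhalation) and one after score. If ratings bracketing each inhalation were already collected, the average within-inhalation change may be used instead. Report the mean change with a 95% CI from a paired or repeated-measures contrast, and show the full time profile descriptively.

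The analysis row is written in the past tense. If the contrast was not fixed before the data were seen, label it post hoc. State that change over an uncontrolled procedure is not an estimate of lavender's effect.

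The cost is a few sentences and one re-run on existing data; no new ratings are needed. What is given up is the overall time p-value as the endpoint result.
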